10.2.4.4 Subgroup Analyses

To assess the heterogeneity of treatment effects among subgroups, the primary and secondary endpoints will be summarized descriptively and analyzed by stratification group (with or without presence of pelvic or lower limb fractures).

In addition, forest plots displaying effect estimates and 95% CIs for subgroups and the entire ITT population will be provided for the primary and secondary endpoints.

10.2.5 Pharmacokinetics Analyses

The PK Population will be used for all pharmacokinetics analyses.

The concentration of iodide in plasma (at different time points and doses) will be derived and summarized for each group. The pharmacokinetic analysis will include collections of a concentration-time profile in subjects following dosing with IP. Mean, standard deviation, and coefficient of variation will be calculated at each time point. The pharmacokinetic behavior of plasma iodide will be described for both samples from days 1, 3, and 7 as area under the concentration versus time curve (AUC, AUC $_{inf}$) the maximal concentration (C $_{max}$), trough concentration (Cmin), the time when the maximal concentration is achieved (T $_{max}$), and terminal half-life (T $_{1/2}$) for each subject.

In subjects, at US sites only, who develop acute renal failure and require dialysis during their first 7 days on this study, pre- and post-dose samples will be obtained each day of IP administration while on dialysis as well. This data will be analyzed descriptively in terms of peak and trough concentrations observed and modelled based on sampling times, where possible.

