1.5 Justification for Dose

The selected dosing regimen for FDY-5301 is 1 or 2 mg/kg daily for 7 days and is based on the available safety, efficacy and PK modeling data for FDY-5301.

FDY-5301 is expected to provide clinically significant exogenous reducing capacity when administered to major trauma ICU patients. The systemic inflammatory response which triggers a catabolic state occurs very early following major trauma, but is postulated to last for longer than a day, and perhaps weeks following trauma (Pedroso 2012). For this reason, and given the poor outcomes expected in the ICUAW population, 7-day dosing is proposed to provide reducing capacity for a period long enough to potentially confer clinical benefit. Daily dosing is based on the half-life of FDY-5301 in healthy volunteers of 6 to 8 hours, implying a return to baseline levels after 24 hours.

Up to 10 mg/kg IV of FDY-5301 has been given to healthy volunteers in a phase 1 study without adverse effects, and a single IV bolus dose of 2 mg/kg was well tolerated in the phase 2 AMI reperfusion study in acutely ill subjects. Specifically, thyroid function tests showed similar group means across all groups, with no suggestion of a drug effect. In a published study of healthy volunteers, cumulative doses of 14 mg/kg of sodium iodide (given as daily oral doses of 1 mg/kg for 14 days) were well tolerated. (Robison 1998).

In nonclinical safety testing, the NOAEL in a rat 14-day repeat dose GLP toxicity study was 74 mg/kg/day and the NOAEL in a GLP dog 7-day repeat dose study was 20 mg/kg/day. These data support daily dosing in subjects at the high dose in this study of 2 mg/kg for up to 7 days.

The PK profile of FDY-5301 has been well characterized in humans. Following IV administration, a rapid maximal concentration (C_{max}) occurs, followed by rapid initial clearance from plasma, a terminal half-life of 6 to 8 hours, and trough levels approaching zero at 24 hours. Exposure will be adequate for daily administration without accumulation, even in subjects with renal impairment.

Confidential Page 21 of 64

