5 STUDY SCHEDULE

The schedule of assessments for all clinical trial sites is listed in Table 1. The additional schedule of assessments for US clinical trial sites only is listed in Table 2.

All study visits will be calculated from time of first IP dose (Day 1). Month 3 and Month 6 visits will be calculated based on the calendar month (e.g., if Day 1 is February 15th, Month 3 would be May 15th and Month 6 would be August 15th).

Confidential Page 29 of 64

Table 1: Schedule of Assessments

Activity	Screening		In-Hospital										Follow Up Long Term Follow Up			
	J			Day 2ª	Day 3ª	Day 4ª	Day 5ª	Day 6ª	Day 7ª	Day 10ª	Day 14ª			Day 28 If Discharged Earlier	Month 3	Month 6
			(+/-) 24hrs of 1 st IP dose								(+/-) 1 day	(+/-) 1 day	(+/-) 1 day	(+) 2 weeks	(+/-) 1 week	(+/-) 2 weeks
Informed Consent	X											,				
Eligibility Criteria	X															
Estimated Height & Weight	X															
Medical History	X															
Demographics	X															
Physical Examination	X				X				X		X	X	X			
Serum Pregnancy Test	X															
Safety Laboratory Tests	X				X				X		X	X	X	X		
12-lead ECG		Randomization	XcXq		X				X		X		X			
TRISS		izat	X													
IP Administration		E	Χe	Χ ^f	Χ ^f	Χ ^f	Χf	Χ ^f	Χf							
CT Scan of Abdomen	Xa	pue								Xh						
SOFAi		8	X		X		à à		X		X	X	X			
Sit to Stand	26									Х	X	X	X		O.	
СРАх			X		X				X	Х	X	X	X			
MRC-SS							à à		å f				X			
Barthel Index													X		X	X
SF-36v2 Health Survey									à f				X		X	Х
Organ Dysfunction TTR			X	X	X	X	X	X	X	X	X	X	X			
Time of Extubation			X	X	X	X	X	X	X	X	X	X	X		DA .	
Occurrence of Sepsis			X	X	X	X	X	X	X	X	X	X	X			
Discharge & Disposition	2		X	X	X	X	X	X	X	X	X	X	X		X	Х
General Health Inquiry															X	X
Overall Survival	. 00		X	X	X	X	X	X	X	X	X	X	X	χj	X	X
Concomitant Medications	X		X	X	X	X	X	X	X	X	X	X	X	χj		
Adverse Events	X		X	X	X	X	X	X	X	X	X	X	X	χi		1

^aIf being discharged from hospital prior to Day 28, conduct all "Day 28 or Hospital Discharge if Earlier" assessments

ⁱConducted until ICU discharge only

^jMay be conducted by phone

Page 30 of 64

^bAssessments may be conducted up to 2 days prior to discharge if earlier than Day 28

^cUp to 12 hrs pre-dose

d Up to 4 hrs post-dose

^eAs soon as possible and within 48 hrs of FIRST hospital arrival time (i.e. immediately post injury)

f(+/-) 4 hrs using the time of day of first IP dose

^gOnly if performed as standard of care within 48 hrs of first hospital arrival and up to 24 hrs after first IP dose

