^hOnly if still in hospital at Day 10 (+/-) 3 days and screening abdominal CT was performed as standard of care

Table 2: Additional Schedule of Assessments

US Sites Only

Activity	Screening		In-Hospital											Follow Up	Long Term	Follow Up	
														Day 28 If			
		_	_											Day 28 or Hospital	Discharged		
		tion	Day 1	Day 2k	Day 3 ^k	Day 4 ^k	Day 5 ^k	Day 6k	Day 7	Day 10	Day 14	Day 21	Discharge if Earlier	Earlier	Month 3	Month 6	
		iza	(+/-) 24hrs of 1 st IP dose								(+/-)	(+/-)	(+/-)	(+)	(+/-)	(+/-)	
56	100	lon	of 1st IP dose								1 day	1 day	1 day	2 weeks	1 week	2 weeks	
Plasma PK	- PG - CO	and	XIXm		X^lX^m				X^IX^m						PG 08		
Unscheduled Plasma PK ⁿ	100	8		X^IX^m		X^IX^m	X^IX^m	$X^{I}X^{m}$							98		
Blood Biomarkers	100		Xº		X				X						Cit		
Leukocyte Gene Expression	OR .		Xº						X						Cité		

kIf being discharged from hospital prior to Day 7, conduct all Day 7 assessments

Page 31 of 64

¹Up to 4 hrs pre-dose

^mUp to 4 hrs post-dose

[&]quot;If a subject requires dialysis, unscheduled plasma PK samples will be collected pre- and post-dose of each IP administration while on dialysis

^{°(-) 24} hrs up to (+) 4 hrs of first IP dose

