6.1.14 Research Blood Samples (US Sites Only)

Research blood samples will be collected from subjects and shipped to a central laboratory, stored, and batched for analysis. Research samples will be stored no longer than 2 years after the completion of the study and include:

- Leukocyte Gene Expression: gene expression analysis for blood leukocyte gene transcription changes in response to trauma
- Plasma PK: pharmacokinetic analysis measuring the concentration of FDY-5301 in plasma
- Blood Biomarkers: analysis of metabolic, inflammatory, and biochemical markers of muscle damage in blood

Confidential Page 35 of 64

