8.4 Preparation and Administration

The formulation has no preservative and is intended for single use only. Injection solutions will be prepared using aseptic technique and inspected prior to administration. The solution for injection is a clear, colorless solution with no particulate matter.

Preparation of the administered dose will be achieved by adjusting the volume of undiluted solution (calculation is based on IP concentration of 7.2 mg/mL) according to treatment assignment. Dosage is based on the subject's body weight (estimated or actual) at screening.

IP will be administered intravenously by a healthcare professional by bolus injection over no more than 10 minutes. Use of an infusion pump is acceptable provided it can administer the total volume in less than 10 minutes. IP may be administered through a central line as long as the line is flushed prior to and following injection. IP must be administered without mixing with any other IV drugs.

Confidential Page 39 of 64

The first IP administration must occur as soon as possible and within 48 hours of first hospital arrival time (i.e. in case of transfers, use time of arrival to first hospital immediately post injury) and then daily for up to 7 days at approximately the same time each day (±4 hours using the time of day of the first IP administration).

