10 STATISTICS

A separate Statistical Analysis Plan (SAP) will provide additional details for statistical analyses and data displays.

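### Section 10.2.5 plans per-subject AUC, AUCinf, Cmax, Tmax and half-life by day, but the scheduled draws normally give at most one point per dosing interval

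*Combined protocol and SAP*

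**What the plan says.** Section 10.2.5 (Pharmacokinetics Analyses) states that "plasma iodide will be described for both samples from days 1, 3, and 7 as area under the concentration versus time curve". It then lists AUCinf, Cmax, Cmin, Tmax and terminal half-life, to be given for each subject, and speaks of collecting a concentration-time profile after dosing.

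Table 2 in Section 5 marks two plasma PK draws on each of Days 1, 3 and 7. One falls within the 4 hours before the dose; the other is "Up to 4 hrs post-dose". No nominal time is set inside either window. The endpoint list in Section 2 describes the same sampling. Samples are taken at US sites only (Table 2 and Section 6.1.14).

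Dosing is daily for up to 7 days, each dose given "by bolus injection over no more than 10 minutes" (Section 8.4). Section 1.5 reports a rapid peak "followed by rapid initial clearance from plasma, a terminal half-life of 6 to 8 hours, and trough levels approaching zero at 24 hours", and bases daily dosing on a "half-life of FDY-5301 in healthy volunteers of 6 to 8 hours".

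For subjects on dialysis, a Table 2 footnote adds that "unscheduled plasma PK samples will be collected pre- and post-dose of each IP administration while on dialysis". Section 10.2.5 allows modelling where possible for these subjects. It states no model for the others. Section 10 says: "A separate Statistical Analysis Plan (SAP) will provide additional details for statistical analyses and data displays". That separate plan is not part of the supplied text.

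**The concern.** Section 10.2.5 itself refers to two samples per day, so it does not assume an unlisted serial profile. The two draws of one day, however, sit on either side of a dose and describe different doses. A half-life needs at least two points on the same declining curve. AUCinf needs a half-life to extrapolate with. A true Cmax and Tmax after a short bolus need early, timed draws. The schedule normally supplies none of these.

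If the text is followed literally, these parameters will be missing, or values that mainly reflect draw time will be tabulated under standard PK names. A reader could then take differences in draw time for differences in exposure between days or doses. The PK Population does not guard against this, because one evaluable sample is enough to enter it (Section 10.1).

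**Working it through.** **Inputs.** Draw days and windows: Table 2. Daily dosing and injection time: Section 8.4. Half-life h of 6 to 8 hours and rapid early decline: Section 1.5. The plan gives no PK figure to reproduce.

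**Step 1: assign each draw to the dose it follows (routine subject, all 7 doses).**

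| Draw | Dosing interval | Points in that interval |
|---|---|---|
| Day 1 pre-dose | none (baseline) | – |
| Day 1 post-dose | dose 1 | 1 |
| Day 3 pre-dose | dose 2 | 1 |
| Day 3 post-dose | dose 3 | 1 |
| none | doses 4 and 5 | 0 |
| Day 7 pre-dose | dose 6 | 1 |
| Day 7 post-dose | dose 7 | 1 |

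Of six draws, one is baseline and five fall in five different intervals. No interval has two.

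**Step 2: exceptions.**
- Dialysis on all 7 days: two points for each of doses 1 to 6, one for dose 7.
- Discharge before Day 7 moves the Day 7 pair to the discharge day. If the pair surrounds a dose, discharge on Day 2 puts two points in the dose 1 interval, and discharge on Day 4 puts two in the dose 3 interval. Days 3, 5 and 6 give none.
- Stopped or missed doses: Section 4.4 keeps scheduled evaluations going after treatment stops. If the Day 2 dose is missed, for example, the Day 1 post-dose and Day 3 pre-dose draws follow the same dose. The documents do not say whether draws tied to a dose are still taken when no dose is given.

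**Step 3: half-life and AUCinf.** One point gives no slope. With one-phase decay, a single value C at time t implies AUCinf = C × 2^(t/h) × h / ln 2. For C = 1 at t = 2 hours:
- h = 6: 1.26 × 6 / 0.693 = 10.9
- h = 8: 1.19 × 8 / 0.693 = 13.7

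The same observation gives values 26% apart within the stated half-life range. At assumed half-lives of 12 and 24 hours it would give 19.4 and 36.7. The assumed half-life sets the answer.

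**Step 4: Cmax and AUC against draw time.** The shortfall from the initial level is 1 − 2^(−t/h). The share of the 24-hour AUC accrued by time t is (1 − 2^(−t/h)) / (1 − 2^(−24/h)). Each cell gives h = 8, then h = 6.

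| Draw at | Shortfall in observed Cmax | Share of 24-hour AUC before the draw |
|---|---|---|
| 1 hour | 8.3%, 10.9% | 9.5%, 11.6% |
| 2 hours | 15.9%, 20.6% | 18.2%, 22.0% |
| 4 hours | 29.3%, 37.0% | 33.5%, 39.5% |

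These figures use terminal decay only. The rapid initial phase in Section 1.5 would enlarge the Cmax shortfall and raise the AUC shares. As an assumed illustration, if a fast phase makes up 50-80% of the initial level with a half-life of 0.25 to 1 hour, a draw at 10 minutes reads 2.3 to 6.4 times a draw at 4 hours in the same subject. The documents give neither the size of the early phase nor a typical draw time.

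**The case against.** **A model could supply the parameters.** A reader might infer that no analysis plan could deliver the listed values. The documents do not support that. Section 10.2.5 names parameters but no estimation method for routine subjects, and Section 1.5 refers to PK modelling data. The separate SAP could specify a population model and report individual AUC, AUCinf, Cmax and half-life under the same names. What stands is narrower: the values are normally not obtainable directly from the draws, and the supplied text states no model for routine subjects.

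**Steady state could be assumed.** The Day 3 or Day 7 pre-dose level could stand in for the coming trough and be paired with that day's post-dose level. At constant clearance the level before dose 3 is 1 − 2^(−48/h) of steady state, or 98.4% (h = 8) to 99.6% (h = 6), so the idea is not unreasonable. But the plan states no such rule, and it cannot work on Day 1. It also assumes stable clearance in subjects who may develop acute renal failure while still being dosed (Section 4.4.1), and it yields no true Cmax, Tmax or multi-phase AUC.

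**Some subjects do have two points.** It would be too strong to say that no subject can. Step 2 lists the routes, and removing the parameters for everyone would discard usable data. Even so, two points give only a crude slope.

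**Troughs are unaffected.** One might extend the criticism to Cmin. The Day 3 and Day 7 pre-dose draws do observe the trough, if actual sampling times are used.

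**The objective is minor.** This is fair. The listed PK endpoint is plasma iodide concentration, which the schedule delivers. That limits the weight of the point, but it does not make Section 10.2.5 and Table 2 agree.

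**Conclusion.** The point holds for routinely dosed subjects. Section 10.2.5 commits to day-specific, per-subject AUC, AUCinf, Cmax, Tmax and half-life that the Table 2 draws normally cannot support directly. The count of at most one point per interval rests only on the schedule and daily dosing. The 29-37% shortfall at 4 hours rests on one-phase decay at the stated 6 to 8 hours and is an illustration, since actual draw times are unknown.

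The scope is narrow. PK is an exploratory objective sampled at US sites only. A reader might infer damage to the trial's main results, but no primary, secondary or safety conclusion uses these parameters. The separate SAP was not available and may already specify a model; if it does, Section 10.2.5 should say so.

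**What to change.** In Section 10.2.5, with matching SAP text:
- For routine subjects, remove Tmax and the directly calculated day-by-day AUC, AUCinf, Cmax and half-life.
- Report observed pre-dose and post-dose concentrations with actual times relative to dose. Do not label the post-dose value as Cmax. Keep the Day 3 and Day 7 pre-dose levels as troughs.
- Report exposure and half-life only as model-based estimates, from a population PK model that pools subjects and days on actual dose and sample times, and only if the data support it.
- Allow direct interval-based estimates only for subjects with enough points in one interval, for example during dialysis sampling.

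This is a text change with no extra samples. The cost is some modelling work and estimates that depend on the model, or no exposure and half-life estimates for routine subjects if the model is not supported.

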10.2.6 Interim Analysis

No interim analysis is planned for this study.

10.2.7 Sample Size Determination and Power Calculations

Approximately 252 subjects will be randomized in a 1:1:1 ratio to receive either FDY-5301 1 mg/kg, FDY-5301 2 mg/kg, or placebo (i.e. 84 subjects per group).

With 252 subjects (with a drop-out rate of 15%, corresponding to 213 evaluable subjects), using a 2-sided significance level of 0.05 and placebo group mean in CPAx total score at Day 10 of 30, assuming a standard deviation of 12 (Corner 2015 and Raymond 2020), this would provide >90% power if there exists an improvement of 6 points in the CPAx total score in the pooled treatment group (either FDY-5301 1mg/kg or 2 mg/kg) compared with placebo group, (i.e. scores of 36 for FDY-5301 vs. 30 Placebo).

Given the assumption that median expected organ dysfunction recovery time is 7 days for the placebo group and the median expected organ dysfunction recovery time is 4.9 days for the pooled treatment group (Xiao 2011), i.e. an expected relative risk reduction of 30% and a 2-sided log-rank test at a significance level of 0.05, the study would have approximately 70% power if at least 213 events are observed (based on no subject being censored until Day 28).

Confidential Page 49 of 64

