The first primary efficacy endpoint is the CPAx total score at Day 10 (or at hospital discharge, whichever occurs first). As the primary analysis, the treatment comparison of the CPAx total score will be performed using an analysis of covariance (ANCOVA). The model will include CPAx total score at Day 10 (or at hospital discharge, whichever occurs first) as a dependent variable, treatment and stratification category (with or without presence of pelvic or lower limb fractures) as factors, and "baseline" CPAx (the first available datapoint) as a continuous covariate.

The p-values, least-squares means, standard errors, and the 2-tailed 95% confidence intervals for the treatment groups and placebo group will be presented.

The second primary efficacy endpoint, organ dysfunction total TTR until Day 28, will be estimated using Kaplan-Meier estimator and compared using log-rank test at a significance level 0.05.

Sample size determination:

Approximately 252 subjects will be randomized to receive FDY-5301 1 mg/kg, 2 mg/kg, or placebo, in a 1:1:1 ratio. This sample size was established based on a 15% drop-out rate. This sample size provides greater than 90% power to detect an improvement of 6 in the CPAx total score for pooled FDY-5301 (1 mg/kg or 2 mg/kg) compared with placebo (e.g. 36 in pooled FDY-5301 group vs. 30 in Placebo group), assuming a standard deviation of 12 (Corner 2015 and Raymond 2020).

Given the assumption that the median expected organ dysfunction recovery time is 7 days for the placebo group and the median expected organ dysfunction recovery time is 4.9 days for the pooled treatment group (Xiao 2011) (i.e. an

Confidential Page 8 of 64

expected relative risk reduction of 30% and a 2-sided log-rank test at a significance level of 0.05), the study would have approximately 70% power if at least 213 events are observed (based on no subject being censored until Day 28).

The sample size calculations were based on the coprimary endpoints achieving a p-value of <0.05 each.

For secondary endpoints, a sequential analysis will be performed. The continuous secondary efficacy endpoints of MRC-SS and worst SOFA score will be analyzed with an ANCOVA model similar to the one described for the primary endpoint of CPAx total score. The secondary endpoint of overall survival at Day 28 will be analyzed using a Kaplan-Meier approach and a log-rank test, similar to the methodology described for the primary endpoint of organ dysfunction total TTR until Day 28.

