10.2.4.1 Primary Efficacy Analyses

There are two co-primary efficacy endpoints defined in this study:

- CPAx total score at Day 10 (or at hospital discharge, whichever occurs first)
- Organ dysfunction total TTR until Day 28

Both primary endpoints will be compared across treatment groups and tested at the 0.05 level of significance and, by convention, both endpoints must demonstrate statistical significance (i.e., $p \le 0.05$) to conclude treatment superiority for regulatory purposes.

For the first primary efficacy endpoint, CPAx total score at Day 10 (or at hospital discharge, whichever occurs first), the following hypothesis will be tested:

$$H_0$$
: $\mu_{Tp} = \mu_p \ v. s. H_a$: $\mu_{Tp} \neq \mu_p$

Where μ_{Tp} , μ_p denote the CPAx total score at Day 10 (or at hospital discharge, whichever occurs first) in the pooled treatment group (FDY-5301 1 mg/kg and FDY-5301 2 mg/kg combined) and placebo groups, respectively. As the primary analysis, the treatment comparison of the CPAx total scores will be performed using analysis of covariance (ANCOVA). The model will include CPAx total score at Day 10 (or at hospital discharge, whichever occurs first) as dependent variable treatment and stratification category (with or without presence of pelvic or lower limb fractures) as factors; and "baseline" CPAx (the first available datapoint) as a continuous covariate.

The p-values, least-squares means, standard errors, and the 2-tailed 95% confidence intervals for the treatment groups and placebo group will be presented.

Confidential Page 47 of 64

If the difference between the means of the pooled treatment group compared to the placebo group is statistically significant, a step-down procedure will be followed to test the individual FDY-5301 doses compared to placebo. The following testing order of doses will be used:

- 1) FDY-5301 2 mg/kg versus placebo
- 2) FDY-5301 1 mg/kg versus placebo

The same statistical method as for the comparison between the pooled treatment group and placebo will be used.

For the second primary efficacy endpoint, organ dysfunction total TTR, the time will be calculated as date of recovery minus date of treatment start plus 1 day. The time to recovery will be estimated using Kaplan-Meier methodology. The Kaplan-Meier curves will be plotted and the time to recovery will be compared using log-rank test at significance level 0.05. The pooled versus placebo and then step-down analysis procedure will be used.

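### Both coprimary endpoints must be significant, but only single-endpoint powers are stated; on the plan's own inputs the joint power is about 64%, and 213 events means every evaluable subject recovers

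*Combined protocol and SAP*

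**What the plan says.** **Success rule.** For the two coprimary endpoints, section 10.2.4.1 states that "both endpoints must demonstrate statistical significance" before superiority is concluded. The synopsis, under sample size determination, adds: "The sample size calculations were based on the coprimary endpoints achieving a p-value of <0.05 each".

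**Stated powers.** Section 10.2.7 starts from 252 randomised subjects, 84 per arm, "with a drop-out rate of 15%, corresponding to 213 evaluable subjects". For CPAx it assumes 36 versus 30 points, SD 12 and a two-sided 0.05 level, and gives more than 90% power for pooled FDY-5301 against placebo. For TTR it assumes medians of 7 days (placebo) and 4.9 days (pooled active), and "a 2-sided log-rank test at a significance level of 0.05". It then states that "the study would have approximately 70% power if at least 213 events are observed (based on no subject being censored until Day 28". The synopsis repeats both figures.

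**Analysis set.** Sections 10.1 and 10.2.4 place all efficacy analyses on the ITT population, which is every randomised subject. Section 10.2.2 allows no imputation for TTR.

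**Not stated.** The protocol gives no probability of winning on both endpoints, no recovery distribution beyond the two medians, and no account of how a death before recovery enters the TTR analysis.

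**The concern.** Two things do not fit together.

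First, the success rule is joint, but the powers are marginal. The chance of winning on both endpoints can never exceed the smaller of the two single-endpoint powers, and it equals that smaller power only if a TTR win always brings a CPAx win. The sizing section nevertheless presents about 70% as what the study would have, next to a figure above 90%.

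Second, the same number does two jobs. The plan arrives at 213 evaluable subjects after drop-out, and then conditions the TTR power on at least 213 recoveries. Counted on the evaluable set, that is 100% recovery by Day 28. Under section 6.1.3 and Appendix 4, recovery requires five organ systems to meet their criteria with no later failure.

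What is at stake is how the result is read. If both assumed effects are real, a trial with about 64% joint power still misses its criterion about one time in three. Someone who takes the power to be 70% to over 90% would give a miss more weight as evidence of no effect than it deserves.

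**Working it through.** **Inputs (section 10.2.7).** 252 randomised 1:1:1, so pooled active to placebo is 2:1. Drop-out is 15%: 84 × 0.85 = 71.4, taken as 71 per arm, which gives 213 evaluable (142 versus 71). CPAx difference 6, SD 12. Medians 4.9 and 7 days, so the hazard ratio is taken as 4.9/7 = 0.7. Two-sided 0.05 for each test.

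**Step 1: reproduce the CPAx power.** Noncentrality = 6 / (12 × √(1/71 + 1/142)) = 6 / 1.744 = 3.44 on 211 degrees of freedom. The noncentral t gives 92.8% (normal approximation 93.1%). The stated figure above 90% holds.

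**Step 2: reproduce the TTR power.** Schoenfeld: power = Φ(√(d·p·(1−p)) × |ln HR| − 1.96), with d = 213 and p = 1/3. √(213 × 2/9) = 6.880, and 6.880 × 0.3567 = 2.454. Φ(2.454 − 1.960) = Φ(0.494) = 68.9%. The stated 70% holds as an approximation.

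**Step 3: power for the declared criterion, granting all 213 events.**
- Independent endpoints: 0.928 × 0.689 = 64.0%.
- Correlation 0.5 between the test statistics (bivariate normal): about 67%.
- Upper bound under any dependence: the smaller marginal, 68.9%.
- Lower bound under any dependence: 0.928 + 0.689 − 1 = 61.7%.

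**Step 4: how many events to expect.** Assume exponential recovery through the stated medians; this shape is not in the plan. Recovered by Day 28:
- placebo: 1 − 2^(−28/7) = 93.75%
- active: 1 − 2^(−28/4.9) = 98.1%

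From 213 evaluable: 71 × 0.9375 + 142 × 0.981 = 205.9 events. The chance that all 213 recover is 0.9375^71 × 0.981^142, about 0.0007. From all 252: 84 × 0.9375 + 168 × 0.981 = 243.6 events. If 15% of the 252 are censored at a constant rate over 28 days, about 234. If that 15% contribute no events at all, 0.85 × 243.6 = 207.

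**Step 5: carry these through.**

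| Basis | Events | CPAx power | TTR power | Joint, independent | Joint, maximum |
|---|---|---|---|---|---|
| 213 evaluable, all recover (the plan) | 213 | 92.8% | 68.9% | 64.0% | 68.9% |
| 213 evaluable, exponential | 206 | 92.8% | 67.5% | 62.6% | 67.5% |
| 252 for TTR with 15% censored steadily; 213 for CPAx | 234 | 92.8% | 73.0% | 67.7% | 73.0% |
| 252 for both, no drop-out | 244 | 96.1% | 74.7% | 71.8% | 74.7% |

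Simulated log-rank tests gave 66.9%, 71.7% and 73.1% for the last three rows, so the Schoenfeld values are slightly favourable.

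The loss from 213 to 206 events is only about 1.4 points of joint power (64.0% to 62.6%). Most of the gap between about 70% and about 63% comes from having to win on both endpoints.

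**The case against.** The strongest reply is that nothing is miscalculated or hidden. The TTR sentence is conditional on its event count and names its censoring premise, and both powers reproduce. A careful reader who combines the success rule with the 70% can see that overall power cannot be higher. This stands: there is no arithmetic error in section 10.2.7. It does not supply the missing figure, because the section never states the power for the rule the trial is judged by.

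A reader might infer from the double use of 213 that the required events are out of reach. The documents do not support that. The evaluable count appears in the CPAx sentence, while TTR is analysed in all 252 randomised subjects, where about 244 recoveries are expected with full follow-up and about 234 with steady 15% censoring. The 206 also rests on the exponential shape. A Weibull with shape 1.5 and the same medians gives 212.7 of 213, although the hazard ratio would then be 0.7^1.5 = 0.59 and no longer the 0.7 that reproduces the stated power.

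The CPAx figure here is unadjusted, whereas the planned ANCOVA includes baseline CPAx. With an assumed baseline correlation of 0.5, CPAx power is about 98% and joint power at 213 events is 0.98 × 0.689 = 67.5%. Even with certain success on CPAx, the joint figure is only the TTR power of 68.9%. The adjustment narrows the gap but does not close it.

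**Conclusion.** Wrong as written, in the sense that the stated power does not match the declared success criterion. At 142 versus 71 evaluable subjects and 213 events, power for the both-must-win rule is about 64% under independence, about 67% at correlation 0.5, and at most 69%. These figures use the plan's own effect sizes, a hazard ratio equal to the ratio of medians, and unadjusted CPAx power.

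The event count is a second, smaller point. Read against the evaluable set, 213 events requires complete recovery by Day 28, and section 10.2.7 does not connect the count to the ITT population. Depending on how drop-outs contribute, joint power under independence runs from about 63% (206 events) to about 72% (252 subjects for both endpoints), given exponential recovery.

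A reader might go further and subtract deaths or permanent non-recovery to reach a much lower figure. Deaths before recovery would lower the event count, but the documents give no rate and do not say whether the 15% drop-out already includes deaths. That reduction therefore cannot be sized from them.

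**What to change.** In section 10.2.7 and in the synopsis:

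1. Add the joint power for the both-must-win rule: about 64% under independence at 213 evaluable subjects and 213 events, and at most 69%. Give the range of about 63% to 72% under independence according to how drop-outs contribute, with the assumptions beside it. Keep the two single-endpoint figures, labelled as such.
2. Derive the expected number of recoveries by Day 28 from the ITT set that will be analysed. State the assumed recovery distribution and how drop-outs are censored, and note that deaths before recovery would reduce the count. Separate this number from the evaluable sample size used for CPAx.

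The cost is protocol and SAP wording, and a headline figure less favourable than the present one. Enrolment, endpoints and tests do not change.
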